- ✓ Adults over 50

Research Support/Funding

Will an existing internal account be used to support the project?

Yes

Describe internal account

This project will be supported by the miscellaneous research accounts in Columbia University and the RFMH

Is the project externally funded or is external funding planned?

No

Study Location

Indicate if the research is/will be conducted at any of the following

- ✓ NYSPI

This protocol describes research conducted by the PI at other facilities/locations

No

Lay Summary of Proposed Research

Lay Summary of Proposed Research

The global spread of COVID-19 is likely to have wide-ranging mental health consequences. As fear in our society increases, the ability of individuals to cope and to make rational well-informed decisions for themselves and for loved ones may become compromised. Anxiety may lead to increased despair, somatic symptoms, depression, suicidal thoughts, and interpersonal conflict with consequent increased use of health care resources. To allay one's fears, people may seek reassurance from an already over-burdened health care system. In the current context, this may have deleterious consequences for patients, healthcare workers, and

the broader community.

The primary purpose of this study is to determine whether heightened anxiety in the context of COVID-19 can be reduced through web-based interventions. While a certain level of anxiety is appropriate during a pandemic of infection that may have profound consequences to self and others, excessive anxiety can lead to impaired mood, thoughts, and behaviors. After confirming eligibility remotely, we will randomly assign participants to one of three on-line treatments: a) Meditation with psychoeducation; b) Kundalini Yoga with psychoeducation; and c) Psychoeducation alone. All 3 groups therefore will receive psychoeducational material about mental health care, but two of the 3 groups will also receive a mind-body therapy (mindfulness meditation or Kundalini Yoga). This study will recruit participants from throughout the United States.

Our research team is uniquely qualified to conduct this study given its expertise in anxiety disorders (esp illness anxiety and OCD) and infectious disease. Each person's study treatment is 8 weeks with a follow-up assessment at 3- and 6-months post-treatment. Our hope with this study is that all participants will experience a reduction in anxiety and improved psychological health as a result of participation.

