If deemed eligible based on the answers related to I/E criteria, participants will be notified to complete informed consent on Proofpilot's website. Individuals who have questions about the study can email the study coordinator. Once consent is completed, they will then be asked to watch a video to encourage their full participation throughout the 8 weeks. They will then complete the baseline set of assessments prior to randomization.

If deemed ineligible to participate, participants will be encouraged to identify a yoga or meditation group in their community. If deemed ineligible due to suspected COVID-19 symptoms, patients will be advised to contact their local health care provider. Patients who score in the severe range for depression and who are excluded from participation will be advised to contact a local health provider for further evaluation of depression.

Study Procedure

Outcome Measures and other assessments. All participants will complete the baseline self-report questionnaires which assess current symptoms, impact of COVID-19, and additional medical and psychosocial history (including lifetime stressors). The full battery of Primary and Secondary outcome measure battery and COVID Follow-up queries will be conducted at baseline, and weeks 4, 8 (primary outcome), and at 3- and 6-months post-treatment. On a biweekly basis to week 8 (primary outcome time point), patients will complete the primary outcome measures and will be asked about their health status and any change in medication or treatment. In addition, on a daily basis, patients randomized to meditation or Kundalini Yoga will be asked to complete a daily log of their daily meditation/yoga practice.

1. Primary Outcome Measures

1. Symptom-based measures. GAD-7 (generalized anxiety); Whiteley-8 (health anxiety)

Secondary Outcome Measures

1. Symptom-based measures:

- PROMIS sleep disturbance
- PHQ8 (depression)
- SSS-8 (somatic symptoms)
- ERQ (emotion regulation)
- PSS-10 (stress)
- Brief hypervigilance scale

2. Health status: Overall Health in general (1 item)

3. Cognition: Neuro-QOL - Applied Cognition (8 items)

Moderators

Selected demographic variables

COVID-19 Exposure and related variables (“CRISIS” survey)

Intolerance of Uncertainty

Mental Health History

Prior Experience with Mind-body practices

Personal Religiosity or Spirituality (Importance; Identification)

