Guided Meditation. This lasts 11 minutes. It is composed of words spoken over a musical background. In this meditation the subjects are guided to picture a healing force or light, a positive energy field, circulating around and within and through themselves. When this force comes in contact with areas that are troubled or painful, subjects are instructed to visualize the distress as being transformed such that healing takes place. They will complete the 25 minutes of stretching/meditation each day. Each week they will watch a new informational talk on Kundalini yoga. Participants will be asked to maintain a meditation log throughout the 8 weeks. They will be asked to record the number of minutes of meditation and stretching as well as any discomfort they experienced. They will also fill out questionnaires at weeks 2, 4, 6, 8 and at 3- and 6-months post-treatment.

Study Drop-outs. Participants are free to drop-out of the study at any time. We will ask participants in the consent form to complete a set of assessments at the time point that they discontinue from the study and also complete a questionnaire indicating the reason for dropping out.

3-Month and 6-Month Follow-ups. All participants will be asked to complete a follow-up set of assessments at 3- and 6-months post-treatment which will allow us to determine whether treatment gains at week 8 have been sustained and whether the meditation or yoga practice has been continued. The study will not impose any restrictions on the participants after week 8. In other words, participants are then free to pursue other interventions if they wish.

After a study is closed to new enrollment, a feedback questionnaire will be sent to all study participants. The feedback questionnaire consists of two parts:

- **the Treatment Satisfaction Questionnaire (3 questions) and**
- **6 questions about participant's decision to discontinue the study.**

Overall, it takes less than 3 minutes to complete the questionnaire. Participants may choose not to answer any of the questions. Neither of the questions requires to disclose any personal information.

Contact with our research team:

- a. For study-related questions, participants will be able to reach our study coordinator through Proofpilot or through email to our study coordinator
 - b. For clinical emergencies, as described in the consent form, participants should go to the nearest emergency room or be evaluated by their current doctor.

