 - c. Should the clinical assessment of depression after randomization indicate a rating in the severe range, an automatic email will be sent to the study coordinator and members of the team notifying them of the participant's high score. The study coordinator will then email the participant and recommend an evaluation by a local mental health provider. The patient will be asked to complete a follow-up depression rating 2 weeks later. If the score again falls in the severe range, one of our study clinicians will attempt to contact the patient by email or phone to recommend evaluation by a local mental health provider and to discuss withdrawal from the study. Withdrawal from the study will be determined according to the clinician's judgement after speaking with the participant, and assessing the costs/benefits to the participant of continuing with the intervention. This does not preclude the clinician from also making referrals or recommendations regarding additional treatment.
- You can upload charts or diagrams if any

Criteria for Early Discontinuation

Criteria for Early Discontinuation

Participants who develop severe depression during the course of this study that persists on the PHQ8 measure for 2 consecutive assessments will be discontinued from the study if appropriate based on clinical judgement. The patient will be contacted by one of the study physicians either by phone (or email). During this contact the physician will recommend referral to a local mental health provider. The study physician will speak with the participant at this time to determine whether it is in the best interests of the participant to remain in or be withdrawn from the study. Significant worsening of depression will be operationalized as a PHQ8 score (20 or higher) that falls in the severe range on 2 consecutive 1-week ratings.

Assessment Instruments

Create a table or give a brief description of the instruments that will be used for assessment

Measure	# of items	Screen	Baseline	Week 2	Week 4	Week 6	Week 8	3-month FU	6-month FU
COVID-19 exposure/status	2	X							
CRISIS Survey Baseline and Follow-up 3.0	10-30		X	X	X	X	X	X	X
GAD-7	7	X	X	X	X	X	X	X	X
Whiteley 8	8		X	X	X	X	X	X	X
SSS-8	8		X		X		X	X	X
PROMIS Sleep	4		X		X		X	X	X

Disturbance							
Emotion Regulation Questionnaire	10		X	X	X	X	X
Neuro-QOL - Applied Cognition	8		X	X	X	X	X
PHQ-8	8	X	X	X	X	X	X
Brief Hypervigilance Scale	5		X	X	X	X	X
Intolerance of Uncertainty Scale	12		X	X	X	X	X

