All participants in this study will be able to continue during the study with whatever treatment they had been receiving prior to the start of this study. All participants are asked to not start new treatments during the first 8 weeks of the study. However, if medically or psychiatrically indicated, patients can start new treatments. We ask all patients to record any new treatments received. After the 8 weeks, participants can pursue other treatments as they wish; as a gift for completing our study, all participants will be offered a free subscription to Journey meditation recordings.

For follow-up purposes (3- and 6-months), we will collect information on any/all treatments (e.g., psychopharmacological, psychotherapeutic, mind-body therapies) that participants have engaged in during the post-treatment phase to control for this at the analysis stage.

There is no delay as a result of completing study questionnaires as these can be done on the same day as starting treatment.

Maximum duration of delay to standard care or treatment of known efficacy:
8 weeks

Treatment to be provided at the end of the study

All participants will be offered 8 weeks of Journey meditation at no cost to them.

Clinical Treatment Alternatives

Clinical treatment alternatives

Individuals do not have to participate in this study in order to obtain guidance in meditation or yoga

stretching. Both therapeutic modalities are available elsewhere. Individuals who wish to receive private treatment will be advised to consult with practitioners in their area.

Risks/Discomforts/Inconveniences

Risks that could be encountered during the study period

1. Quiet Meditation can sometimes lead to distress among individuals with a prior trauma history as they may re-visualize or remember the trauma during the quiet meditation.
2. The self-report questionnaires may lead to psychological distress among some individuals.
3. Stretching or postures may lead to discomfort.
4. Individuals are asked to not start new treatments during the course of this study. For patients who may wish to start an optional treatment, the 8 week delay in starting a new treatment may result in delay in receiving a potentially beneficial optional treatment.
5. Treatments in this study may not reduce symptoms of anxiety. There is also the potential risk that symptoms may worsen, because meditation and psychoeducation can increase awareness of body sensations, thoughts and feelings which people may find to be unpleasant.

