Describe procedures for minimizing risks

1. Patients can stop the self-report questionnaires, postures, meditation or any aspect of the psychoeducation component of the study at any point or if distress is excessive
2. Participants whose PHQ8 scores on the 8 item scale indicate severe depression will be emailed and advised to seek mental health consultation. Participants who have a rating of "severe" on the PHQ8 for 2 consecutive assessments will be contacted by a study physician, advised to seek mental health consultation, and if deemed appropriate by the study clinician, withdrawn from the study.
3. Participants will be given a way to contact the study coordinator through ProofPilot. For emergencies, participants are advised in the consent form to go to their local emergency room or health care provider.
4. If discomfort arises during stretching or postures, patients will be told they can stop at any point
5. If a treatment is recommended by a physician as medically necessary, then that treatment is allowed - the participant merely needs to notify us of this change.

Methods to Protect Confidentiality

Describe methods to protect confidentiality

All data collected on the ProofPilot Platform in this online clinical trial is stored in an encrypted manner using Google's cloud hosting services. All of the participant medical information and research data will be kept confidential to the extent permitted by law. There are legal advocacy organizations that have the authority under State law to access otherwise confidential subject records, but they cannot re-disclose this information without a participant's consent. Any research data transmitted or stored electronically will use a number assigned to the participant, not the participant's name. Although the information provided by the participant may be shared in a deidentified manner with researchers who are not part of our University, their private identifying information (such as name, address, date of birth, or any other personal information that could be used to identify the participant) will not be released at any point.

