Primary aim#1	Aim 1: Test whether Kundalini Yoga with psychoeducation results in a significantly greater reduction in anxiety and multi-system symptom severity compared to psychoeducation alone.
Primary aim #2	Aim 2: Test whether a mindfulness meditation practice with psychoeducation leads to a significantly greater reduction in anxiety and multi-system symptom severity compared to psychoeducation alone.
Secondary aims and Exploratory goals:	
Aim 3: To assess whether treatment outcomes are moderated by COVID-19 related variables and personal variables.
 
Aim 4: To assess at the follow-up at month 3 whether patients have continued with the meditation practice and whether gains observed at week 8 have been sustained.
 
Aim 5: To assess whether there is a difference in both primary and secondary outcomes between the Kundalini Yoga and the meditation treatment groups.

Timing of Analysis	Analysis will be performed after the study is stopped for enrollment and a year after to make sure that all participants have finished their participation.
Analysis Population	We conduct analysis of a change score between baseline and week 8 for those who were randomized into one of the study arms and completed active treatment phase.
Missing Data	Missing data is treated as missing at random
Interim Analyses and Data Monitoring	There is no interim analysis for the protocol.
Primary aim#1 analysis	To investigate whether Kundalini Yoga with psychoeducation results in a significantly greater reduction in two primary outcome measures compared to psychoeducation alone, we will compare two groups of completers using one-sided t-test. P-value and estimation parameter value will be provided.
Primary aim#2 analysis	To investigate whether mindfulness meditation practice with psychoeducation leads to a significantly greater reduction in two primary outcome measures compared to psychoeducation alone, we will compare two groups of completers using one-sided t-test. P-value and estimation parameter value will be provided.

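### Symptom worsening is a named risk and anxiety is scored every two weeks in all arms, but the SAP defines no worsening and plans no harm analysis; its only specified tests are one-sided, in completers

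*Combined protocol and SAP*

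**What the plan says.** **The risk.** Item 5 of the protocol's Risks/Discomforts/Inconveniences section first says that the treatments may fail to reduce anxiety, then adds: "There is also the potential risk that symptoms may worsen, because meditation and psychoeducation can increase awareness of body sensations". The Lay Summary states that "All 3 groups therefore will receive psychoeducational material about mental health care", so the named mechanism reaches every arm.

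**The data.** Study Procedures lists the primary outcome measures as "GAD-7 (generalized anxiety); Whiteley-8 (health anxiety"). The Assessment Instruments table schedules both at baseline, weeks 2, 4, 6 and 8, and both follow-ups. PHQ-8 is a secondary outcome in the full battery, which Study Procedures places at baseline, weeks 4 and 8, and follow-up. People who discontinue are asked for a set of assessments and a questionnaire on their reason for leaving. The Kundalini Yoga description has participants log practice minutes "as well as any discomfort they experienced". The psychoeducation arm keeps no practice log.

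**The analysis.** The SAP's Analysis Population row takes the change from baseline to week 8 in randomised participants who completed the active treatment phase. For primary aims 1 and 2, "we will compare two groups of completers using one-sided t-test", with a p-value and an estimate reported. Aims 3 to 5 are listed without a method, and none concerns harm. No row covers worsening, discomfort, adverse events or reasons for drop-out.

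**The concern.** A plan that names a risk and measures it repeatedly should say how often it occurred. Followed as written, this SAP produces no worsening rate in any arm and no interval for excess worsening under either practice.

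Two features of the specified tests add to the gap. A one-sided test for benefit treats an arm that did worse in the same way as an arm that did no better. The completer restriction removes people who worsened and left. The protocol's own procedures for minimizing risks make that exit possible, since a participant may stop any "aspect of the psychoeducation component of the study at any point or if distress is excessive".

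At stake is what the report can say about the safety of two unsupervised online practices in people selected for heightened anxiety. If worsening is never counted, a non-significant benefit test may be read as evidence that the practices are at worst neutral.

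**Working it through.** The plan gives no figure for worsening, so there is none to reproduce. The check asks what the specified analysis can show, and in how many people.

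**Inputs from the documents**
- 256 enrolled; simple 1:1:1 allocation (SAP, Sample size and Randomization rows).
- Drop-out by week 2 of 49%, 52% and 69%, and by week 8 of 71%, 72% and 84%, for psychoeducation, meditation and yoga (Annual Progress section).

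**Assumptions**
- Arm sizes are not given. I take 256/3 = 85.3, about 85 per arm, and show 75 to 95 where it matters.
- The SAP states no alpha. I take 0.05.

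**Step 1. How many people each rule sees** (85 × (1 − drop-out))

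| | Psychoeducation | Meditation | Yoga | Sum |
|---|---|---|---|---|
| Week-8 completers | 85 × 0.29 = 24.7 | 85 × 0.28 = 23.8 | 85 × 0.16 = 13.6 | about 62 |
| Any questionnaire by week 2 | 85 × 0.51 = 43.4 | 85 × 0.48 = 40.8 | 85 × 0.31 = 26.4 | about 111 |

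With 75 to 95 per arm, the yoga figures run from 12 to 15 completers and from 23 to 29 with a week-2 questionnaire. The second row is a ceiling: the progress section counts at least one questionnaire and does not say that it was a GAD-7.

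**Step 2. What zero observed cases would rule out**

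The one-sided 95% upper bound for zero events in n people is 1 − 0.05^(1/n).
- n = 14: 1 − 0.05^(1/14) = 0.193, about 19%.
- n = 26: 1 − 0.05^(1/26) = 0.109, about 11%.
- n = 85 (everyone observed): 0.035, about 3.5%.

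Over 75 to 95 per arm, the yoga bounds are 18% to 22% for completers and 10% to 12% for the week-2 group.

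**Step 3. What the specified test does if a practice is harmful**

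Suppose a practice is truly worse than psychoeducation by 0.5 SD. For yoga (14 against 25) the noncentrality is 0.5/√(1/14 + 1/25) = 1.50. The benefit-sided test then rejects with probability 0.0009, and that rejection would be for benefit. For meditation (24 against 25) the noncentrality is 1.75 and the probability 0.0004. The test has no rejection region for harm.

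Making the test two-sided in the same completers would not be enough. It would reject in the harm direction with probability 0.31 (yoga) or 0.40 (meditation), and it would still compare mean change rather than count individuals who worsened.

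**Step 4. How worsening should be counted**

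Counting a rise at any visit picks up noise and depends on how many visits a person attends. Assume no true change, a correlation of 0.5 between visits and a margin of 1 SD. About 16% then appear worse with one post-baseline visit and 37% with four. With correlation 0.7 the figures are 10% and 26%. An arm with more drop-out attends fewer visits and so has fewer chances to show worsening. Counting at each visit, and once per person at the last available score, avoids this.

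**The case against.** The strongest reply is that harm information is not absent. The anxiety scales are repeated in every arm. Discontinuers are asked for assessments and a reason. A post-study feedback questionnaire asks about the decision to leave. Health status and treatment changes are queried every two weeks, and the annual report confirms serious adverse event reporting. The SAP also promises an estimate, whose sign would show a mean difference favouring psychoeducation. All of this stands. It shows that worsening is detectable in the data. It does not supply a plan to tabulate it, and a mean difference in completers says nothing about individuals who worsened or about those who left.

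Four stronger readings are tempting and are not supported.
- A reader might infer that the trial cannot detect or report harm, or that the yoga log is the only other source. The routes above contradict both.
- A reader might take the 84% yoga drop-out, against 71%, as a sign of harm. No drop-out reasons are reported. Burden is an equally available explanation: about 25 minutes daily for yoga, 15 for meditation, and a handout every two weeks for psychoeducation alone.
- A reader might extend the point to which scores prompt contact with a participant. That is clinical management and no part of this point.
- A reader might expect a between-arm comparison to reveal harm from psychoeducation itself. All arms share it and there is no untreated arm, so no such comparison can.

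One-sided testing and completer analysis are also general weaknesses of the efficacy plan. They matter here only because nothing else in the SAP would count worsening.

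**Conclusion.** The point holds as an omission with a cheap remedy. The protocol names worsening as a risk and collects the scores that would show it; the SAP neither defines worsening nor analyses it. Its only specified tests cannot declare harm, and they rest on about 62 of 256 participants.

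Using all post-baseline scores could raise that to about 111 at most. In yoga, the rate ruled out by zero cases would fall from about 19% to about 11%. These sizes assume near-equal arms and that a week-2 questionnaire included a GAD-7; the documents confirm neither. That harm is concentrated among early leavers is possible but not shown.

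This should be corrected before results are reported. The status page says that only data analysis is ongoing, so there is still room to do so.

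**What to change.** Add a harm section to the SAP that uses data already held.

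1. **Population.** Every randomised participant with any post-baseline GAD-7, including the assessment at discontinuation. State by arm how many have none.
2. **Measure.** The proportion by arm whose GAD-7 rose from baseline by a fixed margin, at each visit and at the last available score, rather than at any visit. Do the same for Whiteley-8 and, where measured, for a PHQ-8 of 20 or higher.
3. **Comparison.** Two-sided 95% confidence intervals for each practice against psychoeducation. State that the by-arm rates only describe change under the shared psychoeducation.
4. **Supporting tables.** Reasons for drop-out by arm. Report log discomfort within arm only, since psychoeducation has no log to compare.
5. **Status of the margin.** If outcomes by arm have already been seen, label it post hoc.

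The cost is SAP wording and a few tables, with no new data. The intervals will be wide, a margin must be chosen, and some apparent worsening will be measurement noise. Last available scores will also tend to fall earlier where drop-out is higher, so they should be read alongside the by-visit table.
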